5.2.3. Analyses for Categorical Endpoints

For Electronic diary symptom measures that have ordinal categorical responses, the values will be converted to numeric values (i.e. 0-4 for fever and 0-7 for other symptoms, where 0 = no symptoms), and analyzed as continuous endpoints according to [Section 5.2.2](#).

5.2.4. Analyses for Time-to-Event Endpoints

N/A.

5.3. Methods to Manage Missing Data

All summaries and analyses will be based on observed data and missing data imputation is not planned.

6. ANALYSES AND SUMMARIES

Throughout the analyses, a participant is defined as symptomatic if they report at least one new or increased symptom in the Electronic diary during the course of the study.

6.1. Primary Endpoint(s)

Change in self-reported symptom scores in the Electronic diary from well to sick in symptomatic participants with RT-PCR confirmed SARS-CoV-2, influenza virus, or RSV; Change in voice features, such as pitch, jitter, harmonicity, entropy, flatness, shimmer from the voice collection as captured by the Electronic diary from well to sick in symptomatic participants with RT-PCR confirmed SARS-CoV-2, influenza virus, or RSV.

6.1.1. Main Analysis

6.1.1.1. Well to Sick

- Estimator: Primary Estimator E1(Section 2.1.1). This estimator is intended to provide a population level estimate of the well state as well as changes in symptoms and voice features from well to sick in symptomatic SARS-CoV-2, influenza virus, or RSV positive participants using Electronic diary.
- Analysis Sets: (a) Participants in Primary Analysis Set (Section 4) who become SARS-CoV-2, influenza virus or RSV positive (at Swab#2) and symptomatic during the study; (b) A subset of (a) who are symptom free at enrollment; (c) A subset of (a) who have symptoms due to chronic pre-existing conditions at enrollment. These analysis sets will be considered as deemed appropriate by data.
- Intercurrent events and missing data: (a) There are no particular intercurrent events considered. Participants who have events that lead to missing data will be included and missing data will not be imputed. (b) Inadequate compliance – data will be used as recorded.
- Statistical Method: Summary statistics and linear mixed effect analyses as described in Section 5.2.2.3. The total symptom score, each symptom and each voice feature will be modelled individually.
- Summaries:
 - a. Descriptive summaries and corresponding plots of the mean/SD will be provided. For linear mixed effect model analyses, estimates for all parameters fixed effect means, standard errors, 90% CIs, and p-values, as well as the variance estimates for their

random effects will be provided (as described in [Section 5.2.2.3](#)). Results from all models will be presented in a table.

- b. To assess the well-to-sick analysis baseline: For voice features that are determined as statistically significant based on linear model mixed effect analysis, the difference of the voice feature values between every pre-symptomatic day (starting from enrollment day) and the well-to-sick baseline (i.e. 7-day average before symptomatic onset as described in [Section 5.2.2.3](#)) will be computed. The mean/SD of the differences across participants in the analysis set will be plotted by day up to the symptomatic onset.

6.1.1.2. Well State

- Estimand: Primary Estimand E1 ([Section 2.1.1](#)).
- Analysis Sets: (a) Primary Analysis Set ([Section 4](#)). (b) A subset of (a) who are symptom free at enrollment; (c) A subset of (a) who have symptoms due to chronic conditions at enrollment. These analysis sets will be considered as deemed appropriate by data.
- Intercurrent events and missing data: (a) There are no particular intercurrent events considered. Participants who have events that lead to missing data will be included and missing data will not be imputed. (b) Inadequate compliance – data will be used as recorded.
- Statistical Method: Summary statistics and mixed effect analyses as described in [Section 5.2.2.4](#). The total symptom score, each symptom and each voice feature will be modelled individually.
- Summaries: Descriptive summaries, and for mixed effect model estimates of the overall mean value per feature, its standard error, and 90% CI, as well as the variance components will be presented.

6.1.1.3. Correlation of Symptoms and Voice Features

- Estimand: Primary Estimand E1([Section 2.1.1](#)).
- Analysis Sets: (a) Participants in Primary Analysis Set ([Section 4](#)) who become SARS-CoV-2, influenza virus, or RSV positive (at Swab#2) and symptomatic during the study; (b) A subset of (a) who are symptom free at enrollment; (c) A subset of (a) who have symptoms due to chronic conditions at enrollment. These analysis sets will be considered as deemed appropriate by data.
- Intercurrent events and missing data: (a) There are no particular intercurrent events considered. Participants who have events that lead to missing data will be included and missing data will not be imputed. (b) Inadequate compliance – data will be used as recorded.

- Statistical Method: MMRM model, and Pearson and Spearman rank order correlations, as described in [Section 5.2.2.5](#).
- Summaries: Estimates of the coefficient for the change in voice features, standard errors, 90% CIs, and p-values will be summarized. Results from all models and the correlations will be presented in a table. Correlation plots will be presented.

6.1.2. Sensitivity/Supplementary Analyses

Sensitivity analyses may be conducted to assess the effect of compliance. Participants who have less than 3 out of 7 days of baseline data prior to symptom onset will be excluded and analyses in [Section 6.1.1](#) repeated.

6.2. Secondary Endpoint(s)

Estimand: The estimand for all secondary endpoints is based on Estimate E2 ([Section 2.1.2](#)), which is intended to provide a population level estimate of the percentage of occurrence for the secondary endpoints.

Analysis Set: The analysis set for all secondary endpoints is based on FAS (as described in [Section 4](#)).

Intercurrent events and missing data: (a) There are no particular intercurrent events considered. Participants who have events that lead to missing data will be included and missing data will not be imputed. (b) Inadequate compliance – data will be used as recorded.

Statistical methods and summaries for each of the secondary endpoints are detailed below.

6.2.1. Percentage of total days of symptoms and total days of voice recordings entered in the Electronic diary

For each participant, compute:

- a. Symptom compliance = number of compliant days* of symptoms entered in the Electronic diary divided by the total number of days in the study, and expressed as a percentage. Compute mean, SD, median, maximum and minimum percentage of days of symptoms across participants.
- b. Voice compliance = number of compliant days* of completed voice recordings entered in the Electronic diary divided by the total number of days in the study, and expressed as a percentage. Compute mean, SD, median, maximum and minimum percentage of days of completed voice recordings across participants.
- c. Partial voice compliance = number of compliant days* of partially completed voice recordings entered in the Electronic divided by the total number of days in the study, and expressed as a percentage. Compute mean, SD, median, maximum and minimum percentage of days of partially completed voice recordings across participants.

- d. Symptom and voice compliance = number of days* with both symptom compliance and voice compliance, divided by the total number of days in the study, and expressed as a percentage. Compute mean, SD, median, maximum and minimum percentage of days of symptoms across participants.

*Since participants may complete the Electronic diary multiple times per day, a compliant day will be counted as valid and included in these analyses if participants have one or more sessions of an Electronic diary completed for symptoms (a. and d.) or completed/partially completed for voice recordings (b., c. and d.).

The analysis set for this analysis will be the FAS (as described in [Section 4](#)), excluding those participants who experienced technical issues due to study operational errors (e.g., received the wrong instructions for self-swabs).

Plots of number of compliant days of completed symptoms, completed voice recordings and partially completed voice recordings along day for all participants will be generated.

6.2.2. Percentage of quality voice recordings based on signal to noise ratio, sound duration and background noise measures

Compute number of days of quality voice recordings (i.e. recordings exceeding signal-to-noise ratio (SNR) and duration thresholds) per task from the total number of voice compliant days (see [Section 6.2.1](#)) per participant, and express as a percentage:

- a. Percentage of voice recordings with P1 'ah' (SNR > 20dB AND duration > 3 sec) OR (SNR <= 20 dB AND Noise Loud = 'N' AND duration > 3 sec)
- b. Percentage of voice recordings with P2 'ee' (SNR > 20dB AND duration > 3 sec) OR (SNR <= 20 dB AND Noise Loud = 'N' AND duration > 3 sec)
- c. Percentage of voice recordings with P3 'mm' (SNR > 20dB AND duration > 3 sec) OR (SNR <= 20 dB AND Noise Loud = 'N' AND duration > 3 sec)
- d. Percentage of voice recordings with Reading Task (SNR > 20dB AND duration > 10 sec) OR (SNR <= 20 dB AND Noise Loud = 'N' AND duration > 10 sec)
- e. Percentage of quality voice recordings

In the case of multiple Electronic diary sessions per day, the session with the highest quality voice recordings for that day will be used in this analysis.

Compute summary statistics (mean, SD, median, maximum and minimum percentage of days) of these percentages across participants.

6.2.3. Percentage of participants with SARS-CoV-2; and/or Influenza; and/or RSV RT-PCR based positivity in self-swabs

Compute the percentage of participants who:

- (a) Had a valid self-swab #1 result that was positive for
 - a. SARS-COV-2
 - b. Flu A

- c. Flu B
 - d. RSV
 - e. Any of the above (combined)
- (b) Had a valid self-swab #2 that was positive for
- a. SARS-COV-2
 - b. Flu A
 - c. Flu B
 - d. RSV
 - e. Any of the above (combined)

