| Obtain data to characterize the relationship between symptoms and voice features for participants with acute viral respiratory illness. This data will be used as the basis to build voice and symptom algorithm(s) for detection and monitoring of these illnesses. | Change in self-reported symptom scores in the Electronic diary from well to sick in symptomatic participants with RT-PCR confirmed SARS-CoV-2, influenza virus, or RSV. Change in voice features such as pitch, jitter, harmonicity, entropy, flatness, shimmer from the voice collection as captured by the Electronic diary from | | |

| | well to sick in symptomatic participants with RT-PCR confirmed SARS-CoV-2, influenza virus, or RSV. | | |
|--|---|--|--|
| Secondary Objective(s): | Secondary Endpoint(s): | | |
| Assess compliance of the participants using the Electronic diary to collect data. | Percentage of total days of symptoms entered in the Electronic diary. Percentage of total days of voice recordings entered in the Electronic diary. | | |
| Test the quality of the recording from the Electronic diary to collect data that is usable for interpretation. | Percentage of recordings with signal to noise ratio ≥ 20 dB that have duration ≥ 3 sec for phoneme and ≥ 10 sec for reading tasks. | | |
| Determine rates of positivity for SARS- CoV-2/influenza virus/RSV infection. | Percentage of participants with SARS- CoV-2; and/or influenza virus; and/or RSV RT-PCR based positivity in self- swabs. | | |
| Evaluate the feasibility of obtaining self- swabs. | Percentage of participants administering the self-swab at self-swab #1 and self-swab #2. Percentage of participants reporting symptoms in the Electronic diary, who have a self-swab collected at or around symptom onset. Percentage of self-swabs with valid (positive or negative) or invalid (non-reportable due to technical or self-collection failures) results. | | |

Overall Design

This is a low-interventional, observational study with planned enrollment of approximately 8700 participants 18 years of age or older.

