3. RESEARCH QUESTIONS, OBJECTIVES AND ENDPOINTS

| Objectives | Endpoints | | |
|--|---|--|--|
| Primary Objective(s): | Primary Endpoint(s): | | |
| Obtain data to characterize the relationship between symptoms and voice features for participants with acute viral respiratory illness. This data will be used as the basis to build voice and symptom algorithm(s) for detection and monitoring of these illnesses. | Change in self-reported symptom scores in the Electronic diary from well to sick in symptomatic participants with RT-PCR confirmed SARS-CoV-2, influenza virus, or RSV. Change in voice features such as pitch, jitter, harmonicity, entropy, flatness, shimmer from the voice collection as captured by the Electronic diary from well to sick in symptomatic participants with RT-PCR confirmed SARS-CoV-2, influenza virus, or RSV. | | |
| Secondary Objective(s): | Secondary Endpoint(s): | | |
| Assess compliance of the participants using the Electronic diary to collect data. | Percentage of total days of symptoms entered in the Electronic diary. Percentage of total days of voice recordings entered in the Electronic diary. | | |
| Test the quality of the recording from the Electronic diary to collect data that is usable for interpretation. | Percentage of recordings with signal to noise ratio ≥ 20 dB that have duration ≥ 3 sec for phoneme and ≥ 10 sec for reading tasks. | | |
| Determine rates of positivity for SARS- CoV-2/influenza virus/RSV infection. | Percentage of participants with SARS- CoV-2; and/or influenza virus; and/or RSV RT-PCR based positivity in self- swabs. | | |
| Evaluate the feasibility of obtaining self- swabs. | Percentage of participants administering the self-swab at self-swab #1 and self- swab #2. | | |

[figure not shown]
- To describe the safety profile of selfadministered nasal swabs for SARS-CoV-2/influenza virus/RSV RT-PCR among participants.
- Incidence and severity of adverse events (AEs)/research related injuries (RRIs) among all enrolled participants.

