3.2. Secondary Endpoint(s)

The endpoints linked to each secondary objective are as follows:

Endpoints for secondary objective 1: *(a) Percentage of total days of symptoms; (b) Percentage of total days of voice recordings entered in the Electronic diary.*

Endpoints for secondary objective 2: *Percentage of quality voice recordings based on signal to noise ratio, sound duration and background noise measures.*

Endpoints for secondary objective 3: *Percentage of participants with SARS-CoV-2; and/or Influenza; and/or RSV RT-PCR based positivity in self-swabs.*

Endpoints for secondary objective 4: *(a) Percentage of participants administering the self-swab at self-swab #1 and self-swab #2. (b) Percentage of participants reporting symptoms in the Electronic diary, who have a self-swab collected at or around symptom onset. (c) Percentage of self-swabs with valid (positive or negative) or invalid (non-reportable due to technical or self-collection failure) results.*

CCI [REDACTED]

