5.2. General Methods

Data will be summarized using descriptive statistics (number of participants (n), mean, median, standard deviation (SD), minimum and maximum, as appropriate) for continuous (or near continuous) variables, and using frequency and percentages for discrete variables.

Participants can complete the Electronic diary multiple times per day, and each time is considered a session. The session with the most compliant voice and symptom data, and the highest quality voice data will be used for that day to compute the summary statistics. All individual sessions will be used for statistical modeling.

P-values will be generated where appropriate and any p-value < 0.10 will be considered statistically significant. Due to the exploratory nature of the study, p-values will not be adjusted for multiplicity. P-values will be rounded to 3 decimal places and therefore presented as 0.xxx; P-values smaller than 0.001 will be reported as '<0.001'.

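### SAP 6.2.2 passes recordings at or below 20 dB when Noise Loud = 'N', scores days on their best session, and never computes the per-recording percentage defined in Protocol Amendment #1

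*SAP*

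**What the plan says.** The protocol (Sections 1.1 and 3) sets this secondary objective: "Test the quality of the recording from the Electronic diary to collect data that is usable for interpretation". The endpoint is "Percentage of recordings with signal to noise ratio ≥ 20 dB that have duration ≥ 3 sec for phoneme and ≥ 10 sec", where the last figure applies to the reading task. The unit is the recording, and there is no background-noise alternative to the SNR cut-off.

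SAP 3.2 rewords the endpoint as "Percentage of quality voice recordings based on signal to noise ratio, sound duration and background noise measures", with no cut-off in the endpoint text. SAP 6.2.2 then makes it operational:

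- A parenthetical explains quality recordings: "i.e. recordings exceeding signal-to-noise ratio (SNR) and duration thresholds".
- Items a to d pass a recording that meets both thresholds, or one that satisfies "SNR <= 20 dB AND Noise Loud = 'N' AND duration > 3 sec" (10 seconds for the reading task).
- The count is of days, out of the participant's voice-compliant days. The percentages are then summarised across participants.
- Where a day has several sessions, "the session with the highest quality voice recordings for that day will be used in this analysis".

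For modelling, SAP 5.2 states: "All individual sessions will be used for statistical modeling". SAP 5.2.2 adds that voice data failing technical QC are left out where appropriate, but does not link that QC to the rule in 6.2.2.

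According to the SAP's table of changes, version 5 returned to Protocol Amendment #1, the amendment that contains the 20 dB endpoint.

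**The concern.** The parenthetical and the item rules in 6.2.2 do not describe the same set of recordings. A reader of the first would take 20 dB as a requirement. Under the second, it is a requirement only when the noise flag is not 'N'. The noise measure therefore works as a second route to a pass, not as a further condition.

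Three things differ from the protocol endpoint: the criterion, the unit (days instead of recordings) and the choice of session. The protocol's own percentage is not planned alongside.

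The protocol expects the study to document the technology's performance for later interventional use, and this endpoint is one of the direct measures of that. A percentage based on a looser rule and on the best session of the day does not answer how often a home recording meets the protocol's standard. It also may not describe the recordings behind the primary voice results.

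**Working it through.** The plan gives no expected percentage or target for this endpoint, so there is no figure to reproduce.

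**1. The rule.** Let A = SNR above 20 dB, N = Noise Loud 'N', D = duration above the threshold. Items a to d read (A and D) or (not A and N and D). This equals D and (A or N). The 20 dB cut-off has no effect whenever the flag is 'N'.

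**2. Protocol and SAP rules side by side (phoneme task).**

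| SNR | Duration | Noise Loud | Protocol | SAP 6.2.2 |
|---|---|---|---|---|
| 15 dB | 3.5 s | N | fail | pass |
| 15 dB | 3.5 s | Y | fail | fail |
| 20 dB | 3.5 s | N | pass | pass |
| 20 dB | 3.5 s | Y | pass | fail |
| 25 dB | 3.0 s | N or Y | pass | fail |
| 25 dB | 3.5 s | N or Y | pass | pass |

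Away from exact boundary values, the two rules differ in one direction only: the SAP passes low-SNR recordings that the protocol fails.

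**3. Size of the criterion effect (assumed inputs).** Let p be the share of recordings above 20 dB and r the share of the rest flagged 'N', with duration met. The SAP pass rate per session is s = p + (1 − p) × r.

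- p = 0.70, r = 0.5: 0.70 + 0.30 × 0.5 = 0.85.
- r = 0.25 to 0.75: 0.70 + 0.075 = 0.775, to 0.70 + 0.225 = 0.925.
- r = 0: no change, 0.70.

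**4. Size of the best-session effect (assumed inputs).** Let f be the share of days with two sessions, taken as independent. The day-level rate is (1 − f) × s + f × [1 − (1 − s)²].

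- Protocol cut-off kept (s = 0.70), f = 0: 70%.
- f = 0.1: 0.9 × 0.70 + 0.1 × 0.91 = 72.1%.
- f = 0.3: 0.7 × 0.70 + 0.3 × 0.91 = 76.3%.
- Both effects together (s = 0.85, f = 0.3): 0.7 × 0.85 + 0.3 × 0.9775 = 88.8%, against 70% under the protocol definition.

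With p from 0.5 to 0.9, r from 0 to 1 and f from 0 to 1, the gap runs from 0 to 50 percentage points. The upper end is p = 0.5 with r = 1.

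**5. What can move the figure the other way.** Besides the boundary values in step 2, averaging changes the weights. With one session a day and no low-SNR recordings accepted, take two participants with 38 of 40 and 1 of 5 passing. The pooled rate is 39/45 = 86.7%, while the mean of the two percentages is (95% + 20%)/2 = 57.5%. Giving every day equal weight, however many sessions it has, is a change of the same kind. The direction for a single task also presumes that the best session is picked for that task. 6.2.2 does not say whether it is picked per task or over all tasks together.

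**The case against.** The strongest reply is that the change is open and allowed. The SAP's table of changes records both the move to strict inequalities and the added noise criterion, and ties them to the quality flags used in the study. Protocol 9.5 lets the SAP modify plans and asks for an amendment only for major changes to primary endpoints. That stands: nothing is concealed and no rule is broken. It does not, however, reconcile the parenthetical with items a to d, or supply the percentage that the governing protocol defines.

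Second, a reader might infer that the SAP figure overstates quality in an absolute sense, or that recordings at or below 20 dB are unusable. The documents do not support that. They contain no evidence either way on usability below the cut-off. Appendix A, Section 4.2.1, makes background noise part of the quality process, with feedback so that participants can correct a recording. A day-level measure of whether acceptable data were obtained is a reasonable thing to report.

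Third, the schedule is one session a day (Protocol 8.1.1). On such days best-session scoring changes nothing, and for each task the day and the recording coincide. Choosing one session per day also follows the general convention for summary statistics in SAP 5.2. A two-session pass rate such as 91% applies to a day of that kind and is not a value of the endpoint.

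Fourth, not every session necessarily enters the models, given the QC exclusion in SAP 5.2.2. So the mismatch with the modelled recordings is possible, not certain.

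**Conclusion.** The point holds as a mismatch between SAP 6.2.2, its own parenthetical and the governing protocol endpoint. Apart from exact boundary values and the weighting effects of averaging, the reported percentage can only equal or exceed the Amendment #1 percentage, and the latter is not planned anywhere.

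The size cannot be determined from the documents. The move from 70% to 85% rests on two assumptions: 30% of recordings at or below 20 dB, and half of those flagged 'N'. With none flagged 'N' and one session a day, the gap is zero. The best-session contribution also depends on how often participants repeat sessions, which is not given.

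This is a descriptive secondary endpoint without a target, test or decision rule, so it should be corrected but does not threaten the primary analysis. The documents support a claim of a different and generally more permissive measure. They do not support a claim that quality is inflated by a known amount.

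**What to change.** In SAP 6.2.2:

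1. Report, per task and over all recordings in all sessions, the protocol percentage: SNR at least 20 dB with duration at least 3 seconds (phonemes) or 10 seconds (reading). Compute it from the stored SNR and duration values. The table of changes indicates that the study's flags use strict inequalities, so pass/fail flags alone may not reproduce the protocol rule.
2. Show the recordings accepted only through Noise Loud = 'N' in a separate row, and state how that flag is defined.
3. Correct the parenthetical so that it matches the rule in items a to d.
4. Keep the noise-adjusted, best-session-per-day percentage as a separately labelled measure, and say whether the best session is chosen per task.

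The cost is a change of SAP wording, a few extra table rows and a possibly less favourable percentage. No new data need to be collected, provided the underlying SNR and duration values were kept.
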